1.0 SPECIFIC STUDY AIMS

Painful peripheral neuropathy (PPN) is a common sequela of chemotherapy that severely impacts the quality of life in cancer patients (1). There is no biomarker, tool, or method to predict the development or progression of painful chemotherapy-induced peripheral neuropathy (CIPN). The pathophysiology of CIPN remains insufficiently understood; current treatment and prevention strategies provide only modest benefit to patients (2). In this study, we will test the utility of the Diode Laser fiber type Selective Stimulator (DLss) (3) in identifying patients at risk of developing PPN.

Small-diameter lightly myelinated A δ and unmyelinated C cutaneous nociceptive fibers transmit pain from the peripheral to central nerve system. A δ and C fibers are divided by sensitivity: heat, mechanical (tactile), and chemical stimulation, and epidermal versus dermal location. In animals and humans, dying back intra-epidermal fibers lead to reduced pain sensitivity, rather than pain, which suggests fiber loss alone is not sufficient to explain the development of neuropathic pain (4-9). In contrast, abnormally high spontaneous activity of nociceptive fibers, specifically dermal C mechano-insensitive (CMi) fibers, is associated with peripheral ongoing neuropathic pain (10-12)(13-15). Therefore, a tool that can measure, track, and predict the development of abnormal function of A δ and C fibers is a critical unmet medical need.

Most diagnostic tests to study nociceptive fibers are able to measure the loss of pain sensitivity in epidermal fibers (4-9). However, these tests are not fiber-type selective (11). Only microneurographic recording is able to separate fiber type and to access single fibers (16). Though due to complexity, microneurography is unpractical in the clinic. In contrast, we developed and patented DLss, which can be used at the bedside to safely and selectively stimulate A δ and C fibers in superficial and deep skin(14-23). Our preliminary DLss data demonstrates that patients with painful CIPN, who have decreased epidermal A δ and C-fiber densities, have increased A δ pain thresholds, while C-fiber thresholds are intact (20). The A δ :C pain threshold ratio was consistently higher in CIPN than healthy volunteers.

Based on these preliminary data, *we propose that the A δ :C pain threshold ratio, as measured by the DLss during chemotherapy, will identify those patients at risk of developing pain during their treatment.* Ultimately, this will help us identify patients who 1) may benefit from a change in their treatment to prevent CIPN and 2) patients who would be the best candidates for interventional trials testing new drugs for the prevention of PPN.

Aim 1: Demonstrate that the A δ :C pain threshold ratio is significantly higher in patients with painful CIPN than in patients with painless CIPN.

Ovarian cancer annually affects about 20,000 women in the US and causes 14,000 deaths (1999–2012 Cancer Incidence and Mortality Data, <http://www.cdc.gov/cancer/ovarian/statistics/>) (24) Ovarian cancer patients' first line chemotherapy regimen is typically a taxane combined with platinum. These drugs are known to cause CIPN neuropathic symptoms in up to 70% of patients; a large portion of those patients develop painful CIPN (25, 26). The combination of taxane with platinum may increase development of CIPN in 1.5 times compared to just taxane application(25). As a result, ovarian cancer patients have a high overall burden of painful CIPN. Though the exact mechanism of nerve damage may differ between taxanes and platinum drugs, they both result in painful CIPN. Here we will examine the underlying shared pathophysiology

of neuropathic pain. We will evaluate the DLss in [64] ovarian cancer patients with painful and painless neuropathy during initial taxane combined with platinum treatment, to determine their A δ :C pain threshold ratios. Presence or absence of pain will be determined via pain questionnaire and numeric pain scale (27). Enrolling 25 patients with painful CIPN and 25 patients with painless CIPN, we will have 80% power to detect a 1.31 fold A δ :C pain threshold ratio.

Aim 2: Determine the A δ :C ratio over time in patients with CIPN.

Our early data suggests a relationship between pain and the A δ :C ratio in patients where pain is a well-established problem. However, the time course for development and sustainment of CIPN (painful and painless) is not well described. Early changes in the A δ :C ratio may predict progression of CIPN during the course of the treatment and which patients will develop long-term neuropathy; or alternatively, the A δ :C ratio may not change until weeks to months after symptoms have developed, analogous to the delay seen in EMG in mild–moderate nerve damage (28). Following patients longitudinally will also allow us to correlate A δ :C ratio changes with the initial ratio, the patient’s perception of pain over time, total dose of taxane and platinum, and possibly, treatments for neuropathic pain. Patients will be offered retesting approximately two weeks after the completion of sixth cycle. A δ :C ratio changes will be correlated with progression of CIPN based on the presence or absence of pain and dose of agents to determine if the A δ :C ratio evolves with symptoms and if a change in ratio predicts the progression to chronic painful neuropathy, chronic painless neuropathy, or resolution of symptoms.

The proposed work will provide valuable information about the development of pain in CIPN caused by common chemotherapies used to treat ovarian, colon, and other cancers. It will provide the basis for a larger study to validate the utility of DLss as a noninvasive bedside test for small-fiber neuropathies and provide a tool for investigators and clinicians to track and predict the development of pain in CIPN.

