3.3 Enrollment

The target enrollment for this study is 25 patients with painful neuropathy symptoms (Group A) that develop during chemotherapy and 25 patients without painful symptoms during chemotherapy treatment (Group B). Final group assignment takes place on study day 1 when the patient takes a pain questionnaire. There are no differences in study activities between Group A and B. The Stanford Women's Cancer Center sees about 150 new cases of ovarian cancer per year, therefore we believe will able to complete enrollment in 12 months. Patients will be stratified into painful versus painless group based on their first pain assessment inventory. Based on the incidence of painful versus painless neuropathy, we anticipate that Group B will complete enrollment first. Should enrollment in Group A be very slow, our team will consider advertising outside of the Stanford Women's Cancer Center. An additional approach is to increase enrollment in Group B and apply an "unbalanced" design which would increase the number of patients in Group B, but still ensure statistical power of 80%. For example, if only 18 patients with pain are identified, enrolling 39 patients without pain will maintain 80% power. If this step is needed, we will amend the IRB as well as this application. Additionally, we will apply for a no-cost extension to the NIH SBIR that is funding the project.

We understand that patients participating in non-interventional, longitudinal, clinical studies may not follow up for a variety of reasons. To address possible drop out, patients will receive higher compensation for participation in the second test, 75 dollars for the first, 125 dollars for the second. A commonly anticipated drop-out rate is 20% (45), leaving us with approximately 40 patients who we anticipate will complete both time points within the study timeframe. However, it is possible that patients in pain (Group A) may be more likely to follow up with the second test, which would help preserve the power of the study.

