4.0 MATERIAL AND METHODS

4.1 Study Design: This is an open-label, non-interventional protocol testing a diagnostic device for the characterization of chemotherapy induced peripheral neuropathy. Patients will be stratified into Group A or Group B after completing the pain questionnaires. *There is no difference in testing protocols between these groups.*

4.2 Study Calendar:

| | Visit | Screening | 1 | 2 |
|---------------|--------------------------------------|-----------------------|--|---|
| | Time Points | -14 days from Visit 1 | 9 weeks from C1D1 of chemo (+/-1 week) | 21 weeks from C1D1 of chemo (+/-2 week) |
| Action | Screening and Consent | X | | |
| | Eligibility | X | | |
| | Demographics | X | | |
| | Medical History | X | | |
| | Cancer History | X | | |
| | Con Meds | X | X | X |
| | Cumulative dose of each chemotherapy | | X | X |
| | Pain Scale | X | X | X |
| | Neuropathic Pain Questionnaire (NPQ) | | X | X |
| | Headache Assessment | X | X | X |
| | DLss Testing | | X | X |

Note that the dose of platinum and/or taxane will be determined by the treating oncologist. No decisions about total dose, dose delays, escalations, or reductions will be made based on testing in this protocol.

4.3 Duration of Participation/Criteria for End of Study:

Patients will be asked to undergo testing on 2 separate days separated by approximately 10-15 weeks. Each study day is anticipated to take no longer than 2 hours.

Patients will be followed until event that occurs first:

- second DLss testing, which will occur 21 weeks +/- 2 weeks after their first dose of chemotherapy for ovarian cancer
- subject withdraws from study
- subject enters hospice
- subject dies
- PI or study staff determine continued participation is detrimental to the patient
- Study is terminated by the investigators or sponsor

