- 7) The pain threshold will be obtained using the “method of levels”, using a series of ascending stimulation from energy that does not evoke sensation (600mA) and increasing by steps of 100mA until the last sensation is recorded as a 30-40 on the 0-100 pain scale. (0= no sensation, 10= definite sensation/pain, 100 worst imaginable pain). The procedure will be repeated three times and the pain threshold will be defined as averaging the readings of the 3 successive stimulations. The selected current will be applied 4 times. At this current, we expect to produce pain 50% of the time, and no pain 50% of the time.
- 8) The area of stimulation will be moved by 5 millimeters between each stimulation according to the grid (see #3).

Study Visit 2 (21 weeks +/- 2 weeks after first dose of chemotherapy for ovarian cancer)

- Concomitant medications as above
- Cumulative chemotherapy dose as above
- Headache assessment as above
- Pain inventories as above
- DLss testing as described above

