5.2 Analysis plan

The A δ :C pain threshold ratio will be recorded for each eligible and evaluable patient for both time points. We will calculate the average value of this parameter for each group (A and B) on a logarithmic scale. Then we will use a standard statistical two side t-test to compare the “A δ :C pain threshold ratio” in the painless CIPN group to the painful CIPN group. We hypothesize that the painful CIPN group will have statistically significantly higher value “A δ :C pain threshold ratio” than those without.

To assess whether the “A δ :C pain threshold ratio” predicts future painful or painless CIPN, we will conduct logistic regression analysis of the binary pain value (pain or no pain) at the time of the second testing (independent variable) on the “A δ :C pain threshold ratio” at the time of the first testing (dependent variable). It will allow us to estimate whether the “A δ :C pain threshold ratio” predicts the chances of a patient to develop pain.

As an exploratory analysis, we will explore if the “A δ :C pain threshold ratio” obtained at

the first testing session predicts an increase in the numeric pain scale at the second testing session.

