5.3 Sample size

The power analysis of the preliminary data presented here was conducted by [name] (Stanford). The analysis was done on the natural logarithm scale and converted back using anti-logarithms. The geometric mean (GM) ratio of chemotherapy was 1.58 times the GM for healthy group. The GM in the diabetic group was 1.38 times the GM of the healthy group. The most variable group (Diabetics) had a standard deviation (log scale) of 0.33 and this value was used for sample size calculations.

These calculations showed that sample size of 25 subjects in each group will have 80% power to detect a 1.31 fold A δ :C pain threshold ratio in patients with painful versus painless CIPN. Based on the analysis of our preliminary data, we expect the effect size to be larger than 1.31.

It is possible that we will have more patients accrued to Group B compared to Group A because uncomfortable patients may not want to participate in as great a number. In this case, we will consider use using an “unbalanced” (“non-symmetrical”) statistical design, i.e. a design with unequal number of subjects in the two groups. If we get fewer than 25 patients with pain we will increase the number of patients in the group without pain to preserve the power of 80% in order to detect the effect size. If this approach is necessary, we will apply for a no-cost extension of the NIH SBIR.

Table 5.1 shows several possible combinations of sample sizes which will assure the power 80% to detect the effect size 1.31. The sample sizes were calculated using SAS 9.14 software, procedure proc power. The calculations are based on the use of a t-test on the natural logarithm scale with a standard deviation of 0.33, detectable effect size 0.24 on the log scale.

| Scenario | Subjects with pain | Subjects without pain |
|----------|--------------------|-----------------------|
| 1 | 25 | 25 |
| 2 | 24 | 26 |
| 3 | 23 | 27 |
| 4 | 22 | 28 |
| 5 | 21 | 29 |
| 6 | 20 | 31 |
| 7 | 19 | 34 |
| 8 | 18 | 37 |
| 9 | 17 | 42 |

Based on the new patient volume in the women’s cancer center, we expect to recruit 50 patients in 12 months. However, should the study require a non-symmetric statistical

method and its clear we will not be able to recruit 59 patients (scenario 9), we will we will request a12 month no-cost extension from the NIH/NCI.

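### Aim 2's correlation of ratio change with the initial ratio is biased below zero by Visit 1 measurement error and should not be tested against zero; the Section 5 analyses are unaffected

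*Combined protocol and SAP*

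**What the plan says.** Under Aim 2 (Section 1.0), longitudinal follow-up will "allow us to correlate A δ :C ratio changes with the initial ratio". The same sentence lists pain over time, total taxane and platinum dose, and possibly neuropathic pain treatment as further correlates. It names no statistic, scale or null value.

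Only two measurements are available. Section 4.3 states: "Patients will be asked to undergo testing on 2 separate days separated by approximately 10-15 weeks". Within a session, Section 4.4 (step 7) averages each threshold: "The procedure will be repeated three times and the pain threshold will be defined as averaging the readings of the 3 successive stimulations". There is no repeat session near Visit 1, and no reliability figure is given.

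Section 5.2 says that the "pain threshold ratio will be recorded for each eligible and evaluable patient for both time points", but none of its analyses uses the change in the ratio. Section 5.1.2 defines the Aim 2 outcome as a Spearman correlation of the first-session ratio with pain at the second test. Section 5.2 adds a logistic regression on the same two variables and an exploratory look at whether the first ratio predicts an increase in the numeric pain scale.

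**The concern.** With two sessions, the change can only be the second value minus the first. Any error in the first value raises the initial ratio and lowers the change by the same amount. A patient whose Visit 1 ratio happened to read high will tend to appear to fall, and one who read low will tend to appear to rise. Zero is then the wrong reference value for the correlation.

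Some error is to be expected. Each threshold is a subjective rating found on a ladder of 100 mA steps, and the ratio carries the error of two thresholds. Averaging three runs reduces noise within a session but not variation between sessions. Without a repeat session, the team could not later separate the artefact from a real effect.

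Aim 2 asks how the ratio evolves and whether its change foretells the course of the neuropathy. High ratios recovering and low ratios worsening is one pattern such a study might look for, and regression to the mean produces it unaided.

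**Working it through.** **Inputs.** Planned enrolment is 25 + 25 = 50, with 20% drop-out (Section 3.3). The log-scale SD is 0.33 (Section 5.3: the most variable group "had a standard deviation (log scale) of 0.33 and this value was used for sample size calculations"). The test is assumed two-sided at 5%, because the documents state no alpha. Reliability R is not in the documents and is varied from 0.5 to 0.95.

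**The plan's own figures.** 50 × 0.80 = 40, which agrees with "leaving us with approximately 40 patients who we anticipate will complete both time points within the study timeframe". For Aim 1, a two-sample t-test with ln(1.31) = 0.270, SD 0.33 and 25 per group gives 80.9% power, in line with the stated 80%. The documents give no figure for the change-versus-initial correlation.

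**Case 1: no patient truly changes.** Let X and Y be the log ratios at Visits 1 and 2, each with variance s² and correlation R.

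- Cov(Y − X, X) = R·s² − s² = −(1 − R)s²
- Var(Y − X) = 2(1 − R)s²
- Corr(Y − X, X) = −(1 − R)/√[2(1 − R)] = −√[(1 − R)/2]

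The SD cancels, so 0.33 does not affect the result on the log scale. At n = 40 the two-sided 5% critical value is |r| = 0.312. Simulation (bivariate normal, n = 40, at least 20,000 studies per row) gives:

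| R (assumed) | Expected r | Significant negative, Pearson | Significant negative, Spearman |
|---|---|---|---|
| 0.5 | −0.50 | 92% | 89% |
| 0.6 | −0.45 | 84% | 79% |
| 0.7 | −0.39 | 71% | 65% |
| 0.8 | −0.32 | 52% | 47% |
| 0.9 | −0.22 | 28–29% | 26% |
| 0.95 | −0.16 | 16% | 15% |

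The nominal rate in that direction is 2.5%.

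**Case 2: patients truly change by differing amounts, independently of their true starting level.** Let the true change have variance v·s², and let R now be the reliability of a single session.

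- Corr(Y − X, X) = −(1 − R)/√[v + 2(1 − R)]
- With v = 0.3 (assumed) and R = 0.9: −0.1/√0.5 = −0.14; simulated false-positive rate about 14%
- With v = 0.3 and R = 0.8: −0.2/√0.7 = −0.24; simulated rate about 32%

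The between-visit correlations here are R/√(1 + v) = 0.79 and 0.70. Reading them as reliabilities in the table would suggest rates near 52% and 71%, which are much too high. The between-visit correlation falls with real divergence as well as with error, and only the error creates the artefact.

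**Check of the usual alternative (Oldham: change against the mean of the two log ratios).** In Case 1 it rejects about 5% of the time. In Case 2, Cov(Y − X, (X + Y)/2) = (Var Y − Var X)/2 = 0.15s². With R = 0.9 the variance of the mean is (1 + 1.3 + 1.8)s²/4 = 1.025s², so r = 0.15/√(0.5 × 1.025) = +0.21, with about 26% rejections. With R = 0.8 it rejects about 20%. Oldham therefore does worse than the raw correlation at 0.9 (26% against 14%) and better at 0.8 (20% against 32%).

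**The case against.** The strongest reply concerns status. The sentence is narrative in the Aims, and Section 5, which sets out the analyses, does not take it up. Aim 2's own closing restatement relates ratio changes to the progression of neuropathy and to dose, and leaves out the initial ratio. This stands, and it limits the reach of the point. It does not remove it: the correlation is a stated intention under a named aim, and because Section 5 is silent, no method there corrects it.

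The second reply is that the large rates rest on assumed reliabilities and on nobody truly changing, although chemotherapy continues between the visits and the protocol itself expects differing courses. This also stands. A reader might infer that this trial has a false-positive risk of up to 92%. The documents supply neither the reliability nor the spread of true change needed to say so.

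Third, a reader might infer that Oldham's method cures the problem. Its 5% rate holds only when the spread does not change between visits, and Aim 2 anticipates that patients will diverge.

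Fourth, that the result would be taken for a biological finding, or would mislead the later study, is inference. The documents give no rule for interpreting this correlation. They also contain no safeguard against that reading.

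**Conclusion.** The point holds for the one correlation named in Aim 2. For any reliability below 1, and with true change unrelated to true starting level, its expected value is negative, so a test against zero is invalid. The sign follows from the algebra; the size depends on quantities the documents do not give. With 40 completers and an assumed two-sided 5% test, the false-positive rate is about 29% to 92% for reliability 0.9 to 0.5 when nobody truly changes. It is about 14% and 32% at reliability 0.9 and 0.8 when true-change variance is 0.3 of the Visit 1 variance.

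A reader might infer that the trial's main conclusions are at risk. The documents do not support that: the Aim 1 t-test, the Aim 2 Spearman correlation, the logistic regression and the exploratory pain-scale analysis use no change in the ratio. Correlating ratio change with dose or pain is not coupled in this way either. The point deserves correction because it is cheap to correct, but it does not threaten the primary analysis or the sample size.

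**What to change.** In Aim 2, remove the initial ratio from the list of quantities to be correlated with ratio change, and state that the raw correlation of change with initial ratio will not be tested against zero or interpreted biologically.

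Where ratio evolution is related to dose or pain course, regress the Visit 2 log ratio on the Visit 1 log ratio plus that factor. A slope below 1 on the Visit 1 log ratio is expected from measurement error alone and should not be read as recovery. Adjustment for a noisy Visit 1 value is also incomplete when the factor is itself associated with the true Visit 1 ratio, as the study hypothesis expects for pain; say so when reporting.

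If dependence of change on starting level is still of interest, report change against the mean of the two log ratios as a descriptive sensitivity analysis only, stating that true divergence between patients produces a positive correlation under that method.

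The cost is a few sentences in Aim 2, ideally mirrored in Section 5.2. No new data, visits or patients are needed, since both ratios are already collected.

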2.0 BACKGROUND AND RATIONALE

Peripheral neuropathy is a common side effect of chemotherapy, occurring in more than 60% of patients at some point during the course of cancer treatment (1). The resulting pain, numbness, and weakness can severely diminish quality of life. For many patients, the development of neuropathy leads to dose reduction or/and treatment delay, which may ultimately impact survival. The mechanisms by which chemotherapy-induced nerve damage ultimately leads to pain are poorly understood. As a result, there is no reliable way to predict which patients will develop irreversible painful chemotherapy-induced peripheral neuropathy (CIPN)(29-31) and consequently, no effective preventative strategy for combating it. The NIH (PA-12-083) has recognized this gap. This SBIR-funded project proposes the use of a new, patented, noninvasive test to interrogate specific subtypes of small diameter nerve fibers in patients with CIPN, addressing the need for an early diagnostic tool and ultimately predicting which patients should be offered early intervention to prevent persistent painful CIPN.

Two types of nerve fibers found within the epidermal and dermal skin layers, lightly myelinated A δ and small unmyelinated C fibers, transmit nociceptive (pain) information. In certain types of painful neuropathy, such as painful diabetic neuropathy and CIPN, there is a dramatic dying back or degradation of these epidermal fibers (6, 32-34). Despite symptoms of pain, these patients have significantly increased pain thresholds when tested with currently available methods, which

primarily activate epidermal fibers, such as the CO₂ laser or contact heat thermodes (6, 7). In experimental models, ablation of the nociceptive fibers leads to loss of pain sensitivity, rather than pain, suggesting *nerve fiber loss alone is not sufficient to explain the development of pain* (35).

In contrast, spontaneous activity of small fibers is associated with painful peripheral neuropathy (PPN) in animals and humans (13-15). Recently, a specific subtype of C fibers, the C mechano-insensitive (CMi) fibers, was found to be spontaneously active in patients with painful CIPN (14) as well as in other types of PPN (16). CMi fibers are located primarily in the dermis, have widely branching afferent arbors, are relatively insensitive to mechanical stimuli, but respond to noxious heat and chemicals (10). When activated, these fibers release chemokines that can cause vasodilation and may, in turn, sensitize surrounding fibers. In a rat model of paclitaxel-induced painful neuropathy, intra-epidermal nerve fiber degeneration was prominent, but deeper sub-epidermal axon bundles, where CMi reside, were spared (36). These characteristics suggest CMi fibers play a critical role in generating peripheral pain in CIPN.

There are several practical limitations to studying small nerve fibers, particularly CMi fibers, in patients suffering from CIPN. Current diagnostic tests are invasive, extremely time consuming, unable to selectively activate small fiber subtypes, or cannot safely stimulate deep fibers. Conventional electromyography and nerve conduction studies only provide information about large fibers. Microneurography can reliably distinguish small fiber types but it requires hours of

invasive testing which is impractical for broad clinical use. Skin biopsy can be used to quantify small fiber density, but does not always correlate with CIPN symptomatology (33, 37). Noninvasive techniques, such as the QST battery (quantitative sensory testing) with radiant heat or contact thermodes or with the LEP (laser evoked potentials) based on CO₂ laser do not selectively activate C versus A δ and can only safely be used to interrogate superficially located fibers (38-40) (see **Figure 1A**). CMi fibers require current densities five times higher than epidermal polymodal nociceptors (11). Similarly, the activation threshold of C polymodal nociceptors

[figure not shown]

Figure 1A. Cross-section of skin demonstrating deep, uniform penetration of the DLss. The CO₂ laser uses energy levels that damage skin when amount of radiant (e.g., non-coherent) heat penetrating beyond the epidermis. Thermal contact required to activate CMi fibers results in surface diodes emit distributive heat and require damaging temperatures that are about 7 °C higher than the levels of heat to active CMi fibers.

(11, 41) Consequently, both electrical and radiant heat stimuli activate C polymodal nociceptors at intensities well below those for activating CMi fibers, rendering them non-selective and of limited use in evaluating CMi status in patients. In other words, currently available psychometric tests do not allow for the assessment of CMi fiber function. Therefore, it is not surprising that both psychometric QST and LEP tests of small diameter fibers are neither recommended nor reimbursed by Medicare and other insurance companies.

In contrast, the Diode Laser fiber type Selective Stimulator (DLss) selectively stimulates A δ

and C fibers at much greater depths than existing techniques, which makes it an ideal method to assess small fiber subtypes separately. Thus, this technology opens the possibility for bedside clinical testing of a broad array of small fiber neuropathies.

Preliminary Work

In a series of 16 patients with PPN (painful diabetic neuropathy and painful CIPN), the DLss A δ fiber protocol revealed significantly increased pain thresholds compared to healthy volunteers, but C-fiber protocol pain thresholds were similar to those recorded in healthy volunteers (20).

[figure not shown]

Figure 1B. Chemotherapy results in damage or dying back of A δ and C nociceptive fibers in the epidermis, while dermal fibers are relatively spared. The DLss can penetrate into the dermis. Sparing the CMi in the presence of damage to A δ results in an increased A δ :C pain threshold ratio.

had a ratio >2 . This was a small non-uniform sample and was not powered to detect a change in ratios *a priori*. These preliminary data suggest a robust difference between patients with painful CIPN and normal patients. *Therefore, we hypothesize that there is a significant relationship between the A δ :C ratio and painful CIPN.*

[figure not shown]

Figure 2. Pain threshold ratio of A δ to C fibers, activated by DLss for 3 patient groups: healthy, painful diabetic neuropathy, and painful CIPN. $P<0.05$, one-way ANOVA.

In this study, we will test the above hypothesis in patients with newly-diagnosed ovarian cancer, who typically

receive a combination of paclitaxel and carboplatin as first-line chemotherapy. Both drugs individually, and in combination, are known to cause painful peripheral neuropathy in a proportion of patients. Paclitaxel and carboplatin cause peripheral nerve injury by different mechanisms, but both ultimately cause neuropathic pain (43). Because the proposed underlying pathophysiology of the pain is shared, we feel comfortable grouping these patients. We propose that using the DLss in patients with CIPN will allow for the assessment of changes in small-fiber pain thresholds and correlation of these changes to painful versus painless states. Additionally, we would like to demonstrate that the DLss correlates with persistent painful neuropathy. Our ultimate goal is to develop a non-invasive, bedside quantitative test for CIPN. For practitioners and patients, this could help avoid the use of more invasive, time-consuming tests, and non-small-fiber oriented testing, such as electromyography. If successful, this diagnostic test will also be relevant to drug testing, to help identify patients who are more likely to benefit from an intervention (44). The DLss could also be used to monitor the results of such trials noninvasively in a clinical and preclinical setting. While this study focuses on ovarian cancer patients, taxane and platinum based regimens are first-line treatment for several cancer types including ovarian, breast, lung, and colon cancer; therefore it is expected that the developed clinical test will be useful for these patients as well (26).

